Statistical Considerations:

Treatment and Primary Outcomes. This is a single-arm phase II trial of autologous virus specific CTLs for CMV reactivation in patients with hematologic malignancies (excluding T cell leukemia and lymphoma) undergoing CMV seronegative matched unrelated donor (MUD), mismatched unrelated or cord blood allogeneic stem cell transplant. Whole blood will be collected and frozen prior to transplant. After documentation of CMV reactivation, defined as CMV at a level ≥ 137 DNA copies/ml by PCR, autologous CMV-specific CTLs will be generated to be infused within 72 hours of CMV reactivation, if the patient has ANC engraftment, no acute GVHD or steroid administration ≤ 0.5 mg/kg dose. All outcomes will be recorded starting from the time of T-cell administration. While the dose of T-cells will vary depending on how many cells can be grown by ex vivo expansion after thawing and prior to administration, the maximum dose will be $10e5$ viable CD3+ T cells/kg. It is anticipated that 20-25 patients per year will be accrued and that approximately 2 patients per month will develop CMV reactivation and thus be eligible to receive autologous CTLs. A maximum of 36 patients will receive autologous CTLs. The two primary endpoints, starting at the time of autologous T-cell administration, will be $T =$ time to non-relapse mortality and $Y =$ [28-day success], where "success" is defined as follows. CMV will be evaluated weekly at 7, 14, 21 and 28 days using PCR. Treatment will be considered a success if the patient does not require initiation of CMV anti-viral therapy. Anti-viral therapy will be started if 1) End-organ disease is documented at any time point after CTL administration 2) Increase in CMV DNAemia $>50\%$ compared with baseline at any time point 3) Decrease in CMV DNAemia $<50\%$ compared with baseline at day 21 after CTL administration and 4) CMV DNAemia >5000 copies/ml at any time point.

Non-relapse mortality is defined as death because of causes other than relapse of the underlying hematological malignancy. Relapse of underlying hematological malignancy will be a competing event for non-relapse mortality. Time to non-relapse mortality is defined as time to non-relapse mortality from date

of stem cell transplantation.

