Treatment Failure Event. Treatment failure event is defined as death, graft failure, or grade 3-4 toxicity secondary to CTL infusion in 6 months after CTL infusion. The Bayesian method of Thall, et al. will be used to monitor non-relapse mortality (regimen-related death, RRD). Assume that $T \sim \text{exponential}$ with median m , and that *a priori* $m \sim \text{inverse gamma}(3, 13.9)$, which has mean 6.96, corresponding to historical probability $\text{Pr}(T < 6 \text{ months}) = 0.45$. The trial will be stopped early if $\text{Pr}(m > 6.96 \text{ months} \mid \text{data}) < 0.0717$. In terms of median of T , the early stopping event is $[m > 6.96 \text{ months}]$, which is equivalent to $[\text{mean}(T) > 10.04 \text{ months}]$ because T follows an exponential distribution.

Early Deaths. If a patient treated for CMV dies from any cause before day 28, or drops out for some reason, that will be counted as a failure when scoring 28-day success. Due to the lack of computer software to jointly model the two different types of death, regimen-related and not regimen-related, which are competing risks, and non-fatal 28-day failure, and implement a design which separates these events, if a death within 28-days is regimen-related, then the design will "double count" the event. Specifically, such a death will be scored as an event in the monitoring rule for m and also as a 28-day failure in the monitoring rule for p . Consequently, the monitoring rules are conservative. It is anticipated, however, that the actual probability of such very early deaths will be very small, so these considerations will not substantively affect trial conduct.

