Operating Characteristics. The design's operating characteristics, with these two early stopping rules both implemented, are given below in Table 7. Due to the lack of computer software to evaluate the two monitoring rules together, (i) it is not possible to obtain achieved sample size distributions, and moreover (ii) it was necessary to compute the overall early stopping probability, given in the last column of Table 1, under the simplifying assumption that p and m are independent parameters, which of course is not true. However, denoting $Sp = [\text{stop due to the rule for } p]$ and $Sm = [\text{stop due to the rule for } m]$, since $\text{Pr}(Sp) = \text{Pr}(Sp | Sm)\text{Pr}(Sm) + \text{Pr}(Sp | \text{not } Sm)(1 - \text{Pr}(Sm))$, if p and m are positively associated, which seems a reasonable assumption, then $\text{Pr}(Sp | Sm) > \text{Pr}(Sp)$ and $\text{Pr}(Sp | \text{not } Sm) < \text{Pr}(Sp)$, so it is unclear precisely how actual association between the two parameters will affect the joint behavior of the two rules. If appropriate computer software were available, this issue could be explored more precisely.

Secondary Outcomes. Additional outcomes will include overall survival time, disease-free survival time, relapse rate, secondary graft failure, and graft-versus-host disease as an ordinal outcome. Each of these variables which will be analyzed as a function of patient covariates using standard statistical methods, including Bayesian survival regression analysis and ordinal regression. Unadjusted event time distributions will be estimated using the Kaplan-Meier method.

Table 7. Operating characteristics of the two early stopping rules.

Scenario	P(Response)	P(Death < 6 Months)	P(Stop Early due to Response Rule)	P(Stop Early due to Death Rule)	P(Stop Early: Overall)
1	0.50	0.45	0.070	0.100	0.163
2	0.30	0.45	0.681	0.100	0.712
3	0.50	0.60	0.070	0.374	0.418
4	0.30	0.60	0.681	0.374	0.800
5	0.50	0.65	0.070	0.648	0.672
6	0.30	0.65	0.681	0.648	0.888

Stopping Rules

The Bayesian decision cut-off for the treatment failure time event is to **STOP** accrual to the trial if $\text{Prob}(\text{median} > 6.96 | \text{data}) < 0.0717$.

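### GVHD is to be analysed as an ordinal outcome with no time window and no rule for patients who die first; a cumulative incidence with death as a competing event should be used

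*Combined protocol and SAP*

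**What the plan says.** The Secondary Outcomes paragraph of Statistical Considerations names overall survival, disease-free survival, relapse, secondary graft failure and "graft-versus-host disease as an ordinal outcome". It continues: "Each of these variables which will be analyzed as a function of patient covariates using standard statistical methods". Two examples of such methods are then named: "including Bayesian survival regression analysis and ordinal regression". GVHD is the only outcome described as ordinal, so the ordinal regression is evidently meant for it. For event times the paragraph adds "Unadjusted event time distributions will be estimated using the Kaplan-Meier method". It gives no GVHD categories, does not separate acute from chronic, sets no time window, and does not mention death or relapse before GVHD.

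Competing events are recognised elsewhere. Under Treatment and Primary Outcomes: "Relapse of underlying hematological malignancy will be a competing event for non-relapse mortality". Early Deaths scores a death before day 28 as a failure for 28-day success, and death is part of the treatment failure event. Neither rule reaches GVHD.

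On mortality, Treatment Failure Event uses an exponential time with a prior for its median "which has mean 6.96, corresponding to historical probability" of 0.45 by 6 months. Table 7 heads the corresponding column "P(Death < 6 Months". The same Treatment Failure Event paragraph also says: "Treatment failure event is defined as death, graft failure, or grade 3-4 toxicity secondary to CTL infusion in 6 months after CTL infusion".

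**The concern.** A GVHD grade can be compared across patients only if each could be observed for the same period. Death ends that observation. A patient who dies early without GVHD has not shown that the infusion was free of GVHD, yet an ordinal analysis must place that patient somewhere or leave the patient out.

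Placed in the lowest grade, the patient counts as the best result. The grade distribution then looks more favourable the more patients die, and a covariate acting on death alone appears to protect against GVHD. Left out, the patient is lost and the grades describe survivors only.

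GVHD is handled as a potential toxicity of the cells, with its own scoring record (Table 5) and list of chronic manifestations (Table 6). The reader of the final report will use this outcome to judge safety.

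**Working it through.** **Inputs from the documents.** Exponential time with reference median 6.96 months; 0.45 by 6 months; at most 36 treated patients.

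**Assumptions, because the plan gives no figures.** Net GVHD risk G by 6 months (the risk if nobody died) of 0 to 50%; constant hazards; GVHD and death independent; GVHD window of 100 days (3.285 months) or 6 months.

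**Step 1: the plan's own figure.** d = ln 2 / 6.96 = 0.0996 per month. 1 - exp(-6d) = 0.4498, which agrees with 0.45. The mean is 6.96 / ln 2 = 10.04 months, as stated.

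**Step 2: states at the end of a window t.** With g = -ln(1 - G)/6:
- died without GVHD = d/(d+g) x [1 - exp(-(d+g)t)]
- alive without GVHD = exp(-(d+g)t)
- dead share of the no-GVHD group = first / (first + second)

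For G = 30% and t = 6: g = 0.0594 and d + g = 0.1590. Died without GVHD = 0.626 x 0.615 = 0.385; alive without GVHD = 0.385; GVHD = 0.230. Of 36 patients, 27.7 have no GVHD and 13.9 of these are dead (50%).

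| Net GVHD risk by 6 months | Dead share, 6-month window | Dead share, 100-day window |
|---|---|---|
| 0% | 45.0% | 27.9% |
| 10% | 46.4% | 28.5% |
| 20% | 48.1% | 29.2% |
| 30% | 50.0% | 30.1% |
| 40% | 52.2% | 31.0% |
| 50% | 55.0% | 32.2% |

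If an assumed GVHD risk of 10-50% falls entirely in the first 100 days, the 100-day share is 29-36%.

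**Step 3: other mortality, 6-month window, G = 0 to 50%.**

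| Six-month mortality | Dead share of the no-GVHD group |
|---|---|
| 0.20 | 20-27% |
| 0.30 | 30-39% |
| 0.45 | 45-55% |
| 0.60 (Table 7) | 60-70% |
| 0.65 (Table 7) | 65-74% |

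**Step 4: a covariate that changes death only.** Two halves of the sample have six-month mortality of 30% and 60% (average 45%) and the same GVHD hazard, with G = 30%.
- At 30% mortality: observed GVHD = 0.5 x (1 - 0.49) = 0.255.
- At 60% mortality: d = 0.1527 and d + g = 0.2122, so observed GVHD = 0.280 x (1 - 0.28) = 0.202.
- Odds ratio = (0.202/0.798)/(0.255/0.745) = 0.74.

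For G = 20% and 40% it is 0.75 and 0.72. For a doubled death hazard with average mortality held at 45%, it is 0.77-0.82 over G = 10-50%; for a tripled hazard, 0.66-0.74.

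**Step 5: against the noise.** With 18 patients per half and G = 30%, the expected cells are about 4.6, 13.4, 3.6 and 14.4. The standard error of the log odds ratio is the square root of (1/4.6 + 1/13.4 + 1/3.6 + 1/14.4), about 0.80. The bias is ln 0.74 = -0.30, or about 0.4 of a standard error.

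**The case against.** The plan is silent here, and silence is not a wrong rule. A reader might infer that it codes dead patients as free of GVHD. No sentence says so: no categories are defined, an ordinal scale can hold a category for death, and the list of standard methods is open-ended. This stands, and the figures above are therefore conditional. It does not close the gap, because the paragraph names ordinal regression and Kaplan-Meier and nothing that deals with death before GVHD.

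A reader might also take it as a consequence of the plan's own numbers that half of the best category would be dead. That needs a 6-month GVHD window, which the plan does not set, and it needs 0.45 to be mortality. Table 7 labels it death, but the Treatment Failure Event paragraph defines a composite with graft failure and grade 3-4 toxicity, and in the same place speaks of non-relapse mortality. A composite would make mortality lower than 0.45; non-relapse mortality alone would make all-cause mortality higher. Either way it is a historical reference for a stopping rule, not a forecast. The plan also expects very early regimen-related deaths to be rare; fewer early deaths than a constant hazard implies would lower the 100-day share.

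A third tempting reading is that any covariate that raises mortality would look protective. That holds only if the covariate leaves the GVHD hazard alone; one that raises both need not. Even then the bias is under half a standard error.

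Finally, the protocol expects a low GVHD risk from these cells, the outcome is secondary, and overall survival is reported beside it. These points limit the importance. They do not remove the mixing: with a 6-month window and GVHD risk near zero, the dead share of the no-GVHD group simply equals the mortality, and an overall survival curve does not show who in that group died.

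**Conclusion.** The point holds in a limited form. The plan commits GVHD to an ordinal analysis without a window and without handling of death or relapse before GVHD. Followed as written, that analysis must leave patients who die GVHD-free in the lowest grade or drop them, and both mislead.

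If they are left in, the dead share of the no-GVHD group is roughly 30% to 50% at 45% six-month mortality, depending on the window, and 20-39% if six-month mortality is 20-30% (6-month window). These ranges rest on assumed GVHD rates, constant hazards and independence of GVHD and death. The covariate bias is modest (odds ratio about 0.72-0.82 for the 30% versus 60% split and the doubled hazard, somewhat stronger for a tripled one) and would be lost in the noise at 36 patients. The practical harm is a GVHD distribution that reads as safer than it is. The change is worth making, but this is not a threat to the trial's main conclusions.

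**What to change.** In the Secondary Outcomes paragraph:

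- Report the cumulative incidence, from infusion to a fixed time, of grade II-IV acute GVHD and separately of chronic GVHD, with death without GVHD as the competing event. Six months is a natural choice, since it is already the horizon for graft failure monitoring, correlative blood samples, the treatment failure event and Table 7. Say also how relapse before GVHD is treated.
- Do not use one minus Kaplan-Meier with deaths censored. In the 30% example it would estimate 30%, where 23.0% of patients would have GVHD.
- Use cause-specific hazards for any covariate analysis and call it exploratory. In that example about 36 x 0.230 = 8.3 patients would have any GVHD, and fewer would have grade II-IV.
- Maximum grade may stay as a descriptive table over the same window, with death without GVHD in its own row and not in grade 0.

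The cost is a change of wording and a little more analysis, with less use of the full severity scale in the regression. Grades and deaths are already to be collected. Because GVHD is recorded as clinically indicated, it should be confirmed that each patient's status is documented up to the chosen time. Primary endpoints and stopping rules do not change.

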The protective role of recipient T cells after transplantation was not investigated in detail until recently because most transplantation protocols eradicate recipient T cells through a combination of the conditioning chemotherapy and an allogeneic effect of the graft. The notion that recipient T cells could survive even early after transplantation was supported by data from pediatric patient population undergoing UCB transplantation and showed that antigen-specific T lymphocytes of recipient origin were detected in patients receiving a transplant with a related donor, after a chemotherapy-based conditioning regimen, and who did not have GVHD(27). Recently, Chalandon et al showed when a T-cell depletion protocol was used that allowed recipient T cells to repopulate the T-cell compartment, the T cells maintained their function even after conditioning that includes total body irradiation. Furthermore, T cells appeared to protect the patient from CMV-related complications. These data support the notion to investigate the use of recipient-derived autologous CTLs for CMV reactivation after allogeneic HSCT especially for patients without the option to use donor-derived CTLs. Recently, Meij et al. showed the feasibility of generating patient-derived autologous CMV specific CTLs using IFN γ -capture system.

In conclusion, alternative strategies to provide safe and effective adoptive therapy for CMV reactivation after HSCT are needed especially in patients with CMV seronegative donors or following the use of UCB where there is no memory T cell response to CMV.

In this study, we will use this original and novel approach of infusing recipient-derived autologous CMV-specific CTLs for the treatment of CMV reactivation following HSCT in CMV seropositive patients.

Eligibility: (List All Criteria)

Inclusion:

- 1) STEP 1: Within 30 days of study entry: Patients with a history of bone marrow disorders including hematological malignancies and aplastic anemia, Myelodysplastic Syndrome (MDS) and Myeloproliferative disorder (MPD) planning to undergo allogeneic HSCT with reduced intensity or myeloablative conditioning regimens.

- 2) Disease status must be complete remission by standard criteria for Lymphoma and Acute Leukemia patients.
- 3) Patients with Myelodysplastic Syndrome (MDS) and Myeloproliferative Disorder (MPD) must have <5% blasts in the bone marrow.

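### Kaplan-Meier is the only unadjusted event-time method named and its scope is left open; if used for relapse or graft failure with competing deaths censored, it overstates incidence

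*Combined protocol and SAP*

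**What the plan says.** Statistical Considerations, Secondary Outcomes, lists "overall survival time, disease-free survival time, relapse rate, secondary graft failure, and graft-versus-host disease as an ordinal outcome". It continues: "Each of these variables which will be analyzed as a function of patient covariates using standard statistical methods, including Bayesian survival regression analysis", with ordinal regression also named. The paragraph closes with "Unadjusted event time distributions will be estimated using the Kaplan-Meier method". The regression methods are named for covariate analyses, so Kaplan-Meier is the only unadjusted event-time estimator in the document.

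Competing risks are recognised in two other places. Treatment and Primary Outcomes states: "Relapse of underlying hematological malignancy will be a competing event for non-relapse mortality". Early Deaths describes two kinds of death as "regimen-related and not regimen-related, which are competing risks", in the context of the monitoring rules. Neither place names an estimator. Nothing says how death is to be handled when relapse or secondary graft failure is summarised.

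**The concern.** A patient who dies without relapse can no longer relapse, and a patient who dies with a working graft can no longer lose it. Kaplan-Meier with those deaths censored estimates incidence in a hypothetical population in which nobody dies first. That figure exceeds the share of patients who actually have the event as soon as one competing death precedes an event of interest.

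At stake is the accuracy of two secondary estimates and whether the trial's own results agree with each other. Disease-free survival fixes the total of relapse plus death without relapse, and an inflated relapse figure would not fit within that total.

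**Working it through.** **Direction.** At each relapse, Kaplan-Meier with deaths censored adds S_R(t−)/n(t) to the estimated incidence, where S_R counts relapses only and n(t) is the number at risk. Aalen-Johansen adds S(t−)/n(t), where S counts relapses and deaths. Since S_R ≥ S, one minus Kaplan-Meier is never the lower of the two, and it is strictly higher once a death precedes a relapse. This needs no assumed rate.

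**Inputs from the plan.** There are at most 36 treated patients (Treatment and Primary Outcomes). Treatment Failure Event gives a median of 6.96 months and a 6-month historical probability of 0.45. This reproduces under the exponential model: 1 − exp(−ln 2 × 6/6.96) = 0.4498.

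**Assumed inputs.** The documents give no relapse or graft-failure rate. I take net 6-month probabilities r of 10% to 40% for relapse and 5% to 10% for graft failure. The 10% relapse case is included because entry is restricted: "Disease status must be complete remission by standard criteria for Lymphoma and Acute Leukemia patients". Competing death d is 10%, 20% or 30%. The plan's 0.45 is added only as an upper-end case. It is attached variously to non-relapse mortality, to death (Table 7) and to a composite: "Treatment failure event is defined as death, graft failure, or grade 3-4 toxicity secondary to CTL infusion in 6 months after CTL infusion". Read as all death, it includes deaths after relapse. Read as the composite, it includes graft failure itself.

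**Formulas** (constant, independent hazards, 6 months):

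- λ1 = −ln(1 − r)/6 and λ2 = −ln(1 − d)/6
- one minus Kaplan-Meier = r
- cumulative incidence: CIF = λ1/(λ1 + λ2) × [1 − exp(−6(λ1 + λ2))]
- relative excess = r/CIF − 1
- excess patients = 36 × (r − CIF)
- standard error = √[CIF(1 − CIF)/36]

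**Worked case, r = 0.30, d = 0.20.** λ1 = 0.05945 and λ2 = 0.03719. The bracket is 1 − 0.70 × 0.80 = 0.44. CIF = (0.05945/0.09664) × 0.44 = 0.2707. The relative excess is 0.30/0.2707 − 1 = 10.8%, which is 36 × 0.0293 = 1.06 patients. The standard error is 0.0741, so the bias is 0.40 standard errors.

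**Relapse grid: CIF / relative excess / excess patients in 36**

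| Competing death | r = 10% | r = 20% | r = 30% | r = 40% |
|---|---|---|---|---|
| 10% | 9.5% / 5.3% / 0.18 | 19.0% / 5.1% / 0.35 | 28.6% / 5.0% / 0.52 | 38.1% / 4.9% / 0.67 |
| 20% | 9.0% / 11.3% / 0.37 | 18.0% / 11.1% / 0.72 | 27.1% / 10.8% / 1.06 | 36.2% / 10.5% / 1.37 |
| 30% | 8.4% / 18.5% / 0.56 | 16.9% / 18.1% / 1.10 | 25.5% / 17.6% / 1.62 | 34.2% / 17.1% / 2.10 |
| 45% (upper-end case) | 7.6% / 32.2% / 0.88 | 15.2% / 31.4% / 1.72 | 23.0% / 30.5% / 2.53 | 30.9% / 29.6% / 3.29 |

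For competing death of 10% to 30%, the bias runs from 0.10 standard errors (r = 10%, d = 10%) to 0.74 (r = 40%, d = 30%). At 45% it runs from 0.55 to 1.19.

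**Secondary graft failure.** For net 5% and 10%, the excess is 0.09 and 0.18 patients at d = 10%, 0.19 and 0.37 at 20%, 0.28 and 0.56 at 30%, and 0.44 and 0.88 at 45%.

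**Simulation check.** In 5,000 simulated trials of 36 patients (r = 0.20, d = 0.45), mean one minus Kaplan-Meier was 0.200 against a mean Aalen-Johansen estimate of 0.152. The first was never below the second.

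**Do the parts add up?** Assume a disease-free survival event is relapse or death without relapse, with one time origin; the plan states neither. At r = 0.30 and d = 0.20, one minus disease-free survival is 1 − 0.70 × 0.80 = 44.0%, made up of 27.1% relapse and 16.9% death without relapse. With one minus Kaplan-Meier for relapse, the parts sum to 30.0% + 16.9% = 46.9%.

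**The case against.** The strongest reply is that the plan states no error. Only overall and disease-free survival are called times in the list, so the closing sentence may cover just those two, where Kaplan-Meier is correct. Relapse is called a rate. Read as a simple proportion with complete follow-up, it would not carry this bias. The list of regression methods is open and serves mixed outcome types. It does not assign survival regression to relapse, and a cause-specific hazard model that censors deaths would be valid in any case. The authors also plainly know about competing risks.

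Much of this stands. A reader might infer that the plan will report biased relapse and graft-failure figures. The documents do not support that, because they do not say Kaplan-Meier will be used for either. What remains is that the sentence has no limit, follows directly on a list containing both outcomes, and has no alternative anywhere in the document. On the narrow reading, relapse and graft failure have no stated unadjusted method at all.

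It is also fair to say that the size is assumed and usually within sampling error. That lowers the priority. The bias is nonetheless always upward and costs almost nothing to avoid.

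**Conclusion.** The point holds as a conditional one of low severity. If the Kaplan-Meier sentence is applied to time to relapse or time to secondary graft failure with competing deaths censored, incidence is overstated. The direction is certain. The size depends on assumed rates, constant independent hazards and a 6-month horizon: for relapse about 5% to 18.5% relative, or 0.2 to 2.1 patients in 36, and at most 0.74 standard errors. For graft failure it is under one patient throughout.

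Two stronger readings should be resisted. The figures of about 30% and up to 3.3 patients rest on the inconsistently labelled 0.45 and are an upper-end illustration, not an expected bias. Nor is there evidence of bias in non-relapse mortality: the plan declares relapse a competing event for it and does not say Kaplan-Meier will be used. The stopping rules and sample size are not affected.

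**What to change.** In Secondary Outcomes, limit the Kaplan-Meier sentence to overall and disease-free survival. Add that relapse (competing event: death without relapse) and secondary graft failure (competing event: death without graft failure) will be estimated by the Aalen-Johansen cumulative incidence estimator with its variance. This takes one sentence and standard software. It needs no new data and changes nothing in the design.

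For consistency with Treatment and Primary Outcomes, report non-relapse mortality by the same estimator with relapse as the competing event. That part needs one step first: the section counts time both from T-cell administration and from transplantation, and the two origins must be reconciled.

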The following examples illustrate how this rule behaves with actual data. The key points in understanding the rule are that (1) each patient's data consist of either the time of the failure event if it occurred, or the patient's current following time if the event has not occurred and (2) all of the information needed by the rule is summarized by two statistics:

Nevents = the total number of events that have occurred

TFU = total follow up time

In general,

- 1) for given Nevents, larger TFU gives a smaller $\text{Prob}(\text{median} > 6.96 | \text{data})$
- 2) for given TFU, larger Nevents gives a smaller $\text{Prob}(\text{median} > 6.96 | \text{data})$

Example 1.

patient 1: event at 20 days

patient 2: followed for 100 days, no event

patient 3: event at 25 days

patient 4: event at 25 days

Nevents = 3, TFU = 170 \rightarrow $\text{Prob}(\text{median} > 6.96 | \text{data}) = 0.066$

Since this is smaller than the fixed decision cut-off .0717, the decision is **STOP**.

Example 2.

patient 1: event at 30 days

patient 2: followed for 100 days, no event

patient 3: event at 50 days

patient 4: event at 40 days

Nevents = 3, TFU = 220 \rightarrow $\text{Prob}(\text{median} > 6.96 | \text{data}) = 0.089$

Since this is larger than the fixed decision cut-off .0717, the decision is **DO NOT STOP**.

Example 3.

patient 1: event at 20 days

patient 2: followed for 100 days, no event

patient 3: followed for 70 days, no event

patient 4: event at 40 days

patient 5: event at 15 days

patient 6: followed for 40 days, no event

patient 7: event at 20 days

Nevents = 4, TFU = 305 \rightarrow $\text{Prob}(\text{median} > 6.96 | \text{data}) = 0.062$

Since this is smaller than the fixed decision cut-off .0717, the decision is **STOP**.

Data Safety Monitoring Board / DSMB at MDACC:

Select the name of the data safety monitoring board (DSMB) monitoring this protocol:
Not Applicable

Please explain:

This study is not randomized nor blinded.

Protocol Monitoring:

Does this protocol have a schedule for interim and final analysis? No

Provide a rationale for no interim analysis.

This study will be continuously monitored per the statistical design.

Protocol Monitoring Plan:

This study will be monitored by the MD Anderson IND Office and a protocol-specific monitoring plan will be followed.

Intellectual Property:

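### The time-to-event stopping rule is written on the median of T but worked without ln 2: Example 2's decision flips, key point 1 is backwards, and Table 7's death column does not describe the written rule

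*Combined protocol and SAP*

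**What the plan says.** Under *Treatment Failure Event* in Statistical Considerations, T is exponential with median m. The prior on m is inverse gamma(3, 13.9), "which has mean 6.96, corresponding to historical probability" Pr(T < 6 months) = 0.45. The section then confirms the scale: "In terms of median of T , the early stopping event is" m > 6.96 months, which it equates with a mean of T above 10.04 months.

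*Stopping Rules* repeats the rule on the median: "The Bayesian decision cut-off for the treatment failure time event is to" stop accrual when the probability that the median exceeds 6.96 is below 0.0717. Its first key point reads "for given Nevents, larger TFU gives a smaller" probability. Three worked examples follow:

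| Example | Events | TFU (days) | Printed probability | Printed decision |
|---|---|---|---|---|
| 1 | 3 | 170 | 0.066 | STOP |
| 2 | 3 | 220 | 0.089 | DO NOT STOP |
| 3 | 4 | 305 | 0.062 | STOP |

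Example 2 is given as "Nevents = 3, TFU = 220", with the conclusion "Since this is larger than the fixed decision cut-off .0717, the decision is" DO NOT STOP.

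In Table 7, the column headed "P(Stop Early due to Death Rule)" gives 0.100, 0.374 and 0.648 at 6-month death probabilities of 0.45, 0.60 and 0.65.

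**The concern.** The definition and the worked examples appear to use different scales. If T has median m, each unit of follow-up enters the posterior multiplied by ln 2. The printed probabilities look as if that factor was dropped.

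This rule monitors a primary endpoint and is the only one that follows events out to 6 months. The 28-day rule sees only early events: a death before day 28 "will be counted as a failure when scoring 28-day success". The plan has no DSMB and no scheduled interim analysis, and relies on continuous monitoring under the statistical design. If the text supports two versions of the rule, the same data can lead to opposite decisions, and the stated operating characteristics cannot be relied on for the rule as written.

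**Working it through.** **1. Inputs.** From *Treatment Failure Event*: inverse gamma(3, 13.9) prior on the median m, threshold 6.96 months, cut-off 0.0717. From *Stopping Rules*: N (events) and TFU (total follow-up) for each example. The plan gives no days-per-month conversion; d = 30 is assumed and 28 to 31 is shown.

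**2. Formula.** An exponential T with median m has hazard ln 2/m, so the posterior of m is inverse gamma(3 + N, 13.9 + ln 2 × TFU). With G(a; x) the gamma distribution function (shape a, unit scale),

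Pr(m > 6.96 | data) = G(3 + N; (13.9 + k × TFU/d)/6.96),

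where k = ln 2 if m is the median and k = 1 if m is treated as the mean.

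**3. Reproducing the plan's figures, then applying its definition (d = 30).** For Example 2:

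- k = 1: (13.9 + 7.333)/6.96 = 3.051, and G(6; 3.051) = 0.0891.
- k = ln 2: (13.9 + 5.083)/6.96 = 2.728, and G(6; 2.728) = 0.0590.

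| Example | Printed | k = 1 | k = ln 2 | k = ln 2, d = 28 to 31 | Decision under written rule |
|---|---|---|---|---|---|
| 1 | 0.066 | 0.0661 | 0.0463 | 0.049 to 0.045 | STOP (unchanged) |
| 2 | 0.089 | 0.0891 | 0.0590 | 0.063 to 0.057 | STOP (plan: DO NOT STOP) |
| 3 | 0.062 | 0.0621 | 0.0340 | 0.038 to 0.032 | STOP (unchanged) |

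All three printed values match with k = 1. With k = ln 2, Example 2 would reach 0.0717 only if a month had about 25 days.

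**4. Which scale the plan states.** With 6.96 as a median, 1 − 2^(−6/6.96) = 0.450 and 6.96/ln 2 = 10.04; both agree with the plan. With 6.96 as a mean, 1 − exp(−6/6.96) = 0.578, not 0.45.

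**5. Stopping boundaries.** Solving Pr = 0.0717 for the largest TFU that still stops, in 30-day months:

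| Events | Written rule (k = ln 2) | As worked (k = 1) |
|---|---|---|
| 3 | 8.80 months (264 days) | 6.10 months (183 days) |
| 4 | 15.90 months (477 days) | 11.02 months (331 days) |
| 10 | 61.9 months | 42.9 months |

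The ratio is always 1/ln 2 = 1.44.

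**6. Key point 1.** For fixed N, a larger TFU increases the argument of G and so raises the probability, on either scale. The plan's own Examples 1 and 2 show this: at 3 events, 170 days gives 0.066 and 220 days gives 0.089. Key point 2 is correct.

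**7. Table 7.** The plan gives no simulation settings for the death column. The simulations assumed 36 patients, 2 infusions per month, exponential T, looks at each infusion or event, and varied burn-in, final follow-up and 6-month capping (1,500 to 10,000 trials per setting). Approximate stopping probabilities:

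| 6-month event probability | Table 7 | Written rule (k = ln 2) | As worked (k = 1) |
|---|---|---|---|
| 0.45 | 0.100 | 0.24–0.35 | 0.04–0.09 |
| 0.60 | 0.374 | 0.76–0.95 | 0.32–0.44 |
| 0.65 | 0.648 | 0.89–0.99 | 0.53–0.68 |

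At 5 infusions per month with looks only at entries, the written rule gives 0.21, 0.69 and 0.84, still above Table 7 throughout.

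**8. Overall column.** Under the plan's independence assumption, scenario 1 is 1 − (1 − 0.070)(1 − 0.100) = 0.163, as printed. Replacing 0.100 by 0.24 to 0.35 gives 1 − 0.93 × 0.76 = 0.29 to 1 − 0.93 × 0.65 = 0.40.

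**The case against.** The strongest reply concerns Table 7. Its look schedule is not stated, and the excess at 0.45 depends on frequent looks. With a single final look the written rule stops with probability about 0.08 to 0.10 at 0.45, no excess over the printed 0.100; with looks every 12 patients it is 0.16. This stands as a caution about the size of the excess at 0.45. It does not rescue the column. The plan specifies continuous monitoring, and even a single final look gives about 0.61 to 0.82 at 0.60, against 0.374.

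It is also fair to say that the source of Table 7 cannot be established. The version without ln 2 comes nearer but never gave 0.100 at 0.45 with repeated looks, so it is a probable source at most.

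Key point 1 is a separate slip of wording. It does not follow from the missing ln 2 and would not alter a computed decision.

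Finally, only one of the three worked decisions changes, the documents do not show which scale the CTC website used, and the protocol's status is terminated. The error may therefore be confined to the text, and any check of the set-up is retrospective. None of this removes the contradiction between the rule and its examples.

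**Conclusion.** The concern holds. The contradiction between the median-scale definition and the worked probabilities is exact and needs no simulation; its only assumption is the month length, and Example 2 becomes STOP for any month of 28 to 31 days. At 3 events and roughly 184 to 264 days of total follow-up, the two versions give opposite decisions. Key point 1 is wrong on the plan's own figures, with no assumption at all.

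Table 7's death column does not describe the written rule under any schedule tried. The size of the gap depends on assumed settings: under repeated looks at 2 infusions per month, stopping at the 0.45 rate is about 2.4 to 3.5 times the printed 0.100. If the written rule is run, Table 7 understates how often it stops. If the rule in the examples is run, it tests against a 6-month event probability of 0.578, not the stated 0.45.

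The mismatch is the same whether non-relapse mortality or the treatment failure event feeds the rule; the text names both. No error in live monitoring is claimed. This must be fixed, because the plan as written specifies two different stopping rules.

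**What to change.** - Put the parameter, cut-off, examples and Table 7 on one scale. For the stated median rule, the posterior is inverse gamma(3 + N, 13.9 + 0.693 × TFU in months), compared with 6.96. Equivalently, use prior inverse gamma(3, 20.05) on the mean (13.9/ln 2 = 20.05), compared with 10.04. State the days-per-month conversion.
- Re-run the operating characteristics and report the look schedule, accrual rate and final follow-up.
- Then either restate Table 7's death and overall columns for cut-off 0.0717, or reset the cut-off in the sponsor's own software to the intended 10% stopping probability at 0.45. In simulation at 2 infusions per month that cut-off fell between 0.018 and 0.027. This is illustrative only, because it rests on assumed settings.
- Replace the three example probabilities, and let Example 2's decision follow from the final cut-off.
- Correct key point 1 to say that, for a given number of events, a larger TFU gives a larger probability.
- Confirm which scale the CTC website set-up uses or used.

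The cost is a re-run of the monitoring software, a wording change in the statistical section and a check of the set-up. No extra patients are needed. The downside is that the stopping probability at 0.45 may look less favourable if cut-off 0.0717 is kept.
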